5.4 Dose Modification

No dose modifications will be allowed on this study.

5.5 Concomitant medication

5.5.1 Acceptable Concomitant Medications

Duvelisib is a moderate inhibitor of CYP3A4 and monitoring of patients on sensitive medications that are CYP3A4 substrates will be required. Please Appendix B for known substrates of CYP3A. Concomitant medication (including prescribed, over the counter, herbal or vitamin supplements) used by the patient prior to 14 days to enrollment are permitted. All medications should be reported to the investigators and recorded in the concomitant medications page.

5.5.2 Prohibited Medications and Food

Patients on strong inducers or inhibitors of CYP3A within 14 days of starting duvelisib are excluded from the study. Concomitant use of medications known to be strong inducers or

Protocol Title: Duvelisib Exposure to Enhance Immune Profiles of T Cells in Patients with Diffuse Large B Cell Lymphoma (DEEP T CELLS)

inhibitors of CYP3A should be avoided unless deemed to be necessary by the PI. In this instance, patients should be carefully monitored for reduced drug efficacy or SAE from drug-drug interaction. Please see Appendix B for known potent inhibitors and inducers of CYP3A. Other anti-neoplastic drugs, radiotherapy and other investigational drugs are prohibited during the study period.

5.5.3 Supportive Medications

Because of increased incidences of PJP pneumonia, patients on study will be provided with PJP prophylaxis while on treatment with duvelisib. Following completion of duvelisib, PJP prophylaxis will be stopped if CD4+ T cell count is greater than 200 cells/microL.

5.6 Study Procedures

Screening Phase:

All screening evaluations must be conducted and reviewed by the primary investigator to confirm that patients meet the eligibility criteria. The following procedures will be performed during the screening visit:

- Informed Consent
- Medical History, Physical Exam, Assessment of Performance Status
- Electrocardiogram (EKG)
- Labs: Complete Blood Count (includes hemoglobin, platelets, and white blood cell count with differential), Comprehensive metabolic panel (includes sodium, potassium, chloride, creatinine, AST, ALT total bilirubin and alkaline phosphatase), Coagulation Testing (PT/INR, PTT), Thyroid Stimulating Hormone (TSH)
- T cell count phenotyping via flow cytometry
- Pregnancy Test (for women of childbearing potential)
- Infectious Work Up: HIV antigen/antibody, Hepatitis C antibody and Hepatitis B antibodies with viral loads (if known history of treated Hepatitis B or C).
- COVID-19 screening by PCR: During the screening period within 7 days of initiation of duvelisib.
 - If asymptomatic and PCR negative: Ok to proceed
 - If PCR+ and:
 - Asymptomatic: Wait 14 days and initiate duvelisib
 - Symptomatic: Wait 14 days *after resolution of symptoms* and initiate duvelisib
 - A negative PCR is not required after a 14 day wait period

Please see section 1.2 (Table 1) for schedule for screening and pre-screening assessments. Pre-screening assessments will be completed within two weeks of initiation of duvelisib treatment.

Treatment Phase:

Procedures to be conducted during the treatment phase of the study are presented in the Schedule of Assessments (Section 1.3, Table 1).

- Brief medical history
- Symptom-directed physical exam

Protocol Title: Duvelisib Exposure to Enhance Immune Profiles of T Cells in Patients with Diffuse Large B Cell Lymphoma (DEEP T CELLS)

- ECOG Performance Status
- Vitals signs, weight
- Review of prior/concomitant medications
- Labs: Complete Blood Count (includes hemoglobin, platelets, and white blood cell count with differential), Comprehensive metabolic panel (includes sodium, potassium, chloride, creatinine, AST, ALT total bilirubin and alkaline phosphatase), Thyroid Stimulating Hormone (TSH)
- T cell count and phenotyping (days 1 and 15 only)
- AE monitoring (days 8 and 15)

Post CAR-T 19 Cell Infusion Assessments

Procedures to be conducted during the post CAR-T 10 cell infusion phase of the study are presented in the Schedule of Assessments (Section 1.3 Table 2).

- CAR T 19 PCR
- CAR T phenotyping
- PET/CT or CT (day 90 only post CAR T)

5.7 Description of Study Procedures

Definition of Study Assessments

All patients will be closely monitored for safety and tolerability throughout the study. Patients will continue dosing until they experience intolerable AE's, patient withdrawal or termination of the study. Patients may be discontinued from study treatment in the following situations: 1) patients has decided to withdrawal from the study, 2) Intolerable adverse events, 3) confirmed disease progression or lack of benefit, 4) pregnancy, or 5) severe noncompliance (including but not limited to receiving less than 75% of duvelisib doses (23/28 doses). The schedule of activities is listed in section 1.3.

Medical History

Medical history and demographics will be collected at screening. Medical history will include other significant co-morbidities, previous surgeries, cancer history, previous chemotherapy and outcomes, use of tobacco, alcohol and recreational drugs and any known toxin exposure. Demographics data will include age, sex and self-identified race/ethnicity.

Performance Status

The ECOG performance status (see appendix A) will be assessed at screening and throughout the study (days 1, 8 and 15 during treatment with duvelisib; days 7,14,28,42 and 90 post CAR-T infusion).

Physical Exam

Physical exam will include examination of all body systems, including assessment of general appearance, weight, height, head, neck, lymph nodes, heart, lungs, abdomen, extremities, skin and nervous system. A physical exam will be performed on screening and on days 1,8 and 15.

Laboratory Data

Blood samples for chemistry, hematology, viral serologies, leukocyte immunophenotyping and pregnancy (for pre-menopausal patients) will be analyzed at Winship Cancer Institute laboratory. The chemistry panel will include sodium, potassium, chloride, bicarbonate, glucose, BUN, AST, ALT, total bilirubin, total protein, thyroid stimulating hormone and magnesium will be tested at screening and on days, 1,8 and 15. Hematology panel includes complete blood count, including white blood cell count with differential (neutrophils, lymphocytes, eosinophils, basophils), red blood cell count, hemoglobin, hematocrit and platelet count will be tested at screening and days 1, 8 and 15. Viral serologies will be tested at screening and include:

- HIV antigen/antibody
- Hepatitis B Panel (HBsAg, HBsAb, HBcAb and HBV DNA PCR if HBcAb is positive)
- Hepatitis C Panel (HCV Ab and HCV PCR if HCV Ab is positive)

Leukocyte immunophenotyping (via flow cytometry/fluorescence-activated cell sorting) will be done at screening and prior to apheresis for manufacturing CAR-T cells. This will determine the amount of B/T/NK cells and more specifically, the phenotypes and frequencies pre and post Duvelisib exposure.

Electrocardiogram

All ECG's will use a 12-lead tracing and performed during screening only. ECG will measure PR interval, QRS interval, RR interval and QTc. Additional ECG's and other cardiac tests can be performed as clinically indicated.

6. Data and Specimen Banking

Blood samples will be obtained and used for medical research by the investigators of this study. *Data and specimens from this study may be useful for other research being done by investigators at Emory or elsewhere. To help further science, Investigators may provide de-identified data and/or specimens to other researchers. Any information that could identify patients will not be included. If data or specimens are labeled with study ID, we will not allow other investigators to link that ID to identifiable information.*

Samples and data collected under this protocol may be used to study lymphoma. Access to stored samples will be limited to IRB-approved investigators. Samples and data will be stored using codes assigned by the investigators or their designees. Data will be kept in password-protected computers. Only investigators will have access to the samples and data.

All stored samples will be maintained in the laboratory to which it was sent initially for analysis. Study patients who request destruction of samples will be notified of compliance with such request and all supporting details will be maintained for tracking.

The results of some study tests and procedures will be used only for research purposes and will not be placed in patient's medical record. For this study, those items include: research blood collection.

7. Tisagenlecleucel Apheresis Phase

7.1 Apheresis Collection

Patients will need to undergo leukapheresis within two (2) days of completion of the 8 to 15 day treatment of duvelisib. Apheresis will be performed at the Emory Center for Transplantation and Cell Therapy. Peripheral blood mononuclear cells will be collected for CAR-T cell manufacturing according to the standard of care. A single 2-4-hour leukapheresis will be performed on the COBE Optia with the intention of harvesting 3×10^9 white blood cells. If patients are unable to collect the necessary amount required for manufacturing, they can undergo a second leukapheresis. If patients are not able to collect enough product after the second leukapheresis, they will be considered unevaluable and replaced. After apheresis, the quantity of CD27/CD28 double positive T cells, CD4/CD8 double negative gamma delta positive T cells and CD4/CD8 double negative gamma delta negative T cells will be measured via flow cytometry. CAR-T cell manufacturing will be provided by Novartis and are expected to be ready 4 weeks after collection. Failure of the incoming apheresis material or outgoing product to meet the commercial specifications will be discussed with Novartis on a case by case basis.

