Protocol Title: Duvelisib Exposure to Enhance Immune Profiles of T Cells in Patients with Diffuse Large B Cell Lymphoma (DEEP T CELLS)

Endpoints:	
Primary Endpoint:
 
• The fold increase in the proportion of T cell phenotypes expressing CD 27/28 (to overall T cell count) after 8 to 15 day exposure to duvelisib 
Secondary Endpoints:
 
• The proportion of duvelisib consumed as evaluated by the patient pill diaries.• Manufacturing time of CAR-T 19 cells in weeks (includes manufacturing failure)• The proportion of CD27/28 double positive T cells and CD4/8 double negative T cells• CAR-T kinetics assessment by PCR• Overall response at 90 days after CAR-T cell infusion defined by the Tumor Response Assessment that are complete responders (CR) and partial responders (PR).• Progression-free Survival (PFS) at 90 days per RECIST 1.1 and Overall Survival at 90 days• ICU transfer due to CRS and/or neurotoxicity or due to the treatment with tocilizumab and/or corticosteroids• Grade III-V toxicities (as defined by CTCAE version 5.0)
Study Population:	20 patients will be enrolled with relapsed/refractory DLBCL or relapsed/refractory follicular lymphoma
Phase:	Pilot
Description of Sites/Facilities Enrolling Participants:	This study will be at Winship Cancer Institute, Emory University.
Description of Study Intervention:	Duvelisib is an oral PI3K inhibitor that is given at a dose of 25mg BID prior to manufacturing of CAR-T cells.
Study Duration:	We estimate that the duration of the study will be approximately 18 months.

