3.1 Study Rationale

Relapsed/Refractory Diffuse Large B Cell Lymphoma (DLBCL) has a dismal prognosis, especially with relapse/refractory disease after autologous stem cell transplantation. Recently, a new adoptive cell transfer therapy, CAR-T cells, that manufactures a patient's T cells to express artificial receptors on their cell surface has shown promising results in patients that relapse or have refractory disease. However, there are subset of patients that fail to manufacture a sufficient amount of CAR-T cells ex vivo, have poor expansion in vivo or lose persistence of their CAR-T cells after infusion. This has been attributed to relapsed/refractory DLBCL patients having a predominance of more differentiated T cells that are senescent and have poor expansion potential for CAR-T cell manufacturing. This pilot study will examine if a 2-week exposure to Duvelisib, will favorably change a patient's T cell phenotype for manufacturing of more potent CAR-T cells for relapsed/refractory DLBCL and relapsed/refractory follicularlymphoma patient receiving commercial tisagenlecleucel.

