17.5.1 Study Design Endpoints

This is pilot study to examine if exposure to a dual PI3K delta and gamma inhibitor before CAR T cell leukapheresis leads to decreases in manufacturing time and enhanced expression of CD27/CD28+ T cells. Patients who receive at least 75% (23/28 doses) of duvelisib will be evaluable for final analysis. Patients who do not receive 75% of doses will be considered unevaluable and replaced. Patients who do not undergo leukapheresis within two (2) days of completion of the 8 to 15 days of duvelisib will be considered unevaluable and replaced. All patients with any exposure to duvelisib will be evaluable for toxicity (please see section 13.3 on grading of toxicities).

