17.5.2 Analysis of Primary Endpoints

All patients that complete >75% of planned duvelisib doses and undergo leukapheresis within 2 weeks of duvelisib treatment completion will be included in the final analysis of the primary endpoint. The primary endpoint of the study to estimate the fold-change increase in CD27/CD28 double positive T cells following *in vivo* exposure to duvelisib from baseline to day 15. Our in vitro studies have shown that culturing DLBCL patients' T cells with 14 days of duvelisib increased the amount of CD27/CD28 double positive T cells from 12.2% to 32.7% (Petersen, et al, supplemental data). However, there are currently no *in vivo* background data to benchmark the expected fold-change CD27/CD28 double positive T cells over a 14-day window. Therefore, with 20 patients, this pilot study will be based on estimation on the fold change increase only and will not include a formal evaluation of the change against a null unpromising fold-change. However, we will consider this study promising if there is at least a two-fold increase in CD27+/CD28+ in at least 75% of patients.

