17.5.3 Analysis of Secondary Endpoints

- 1). Descriptive statistics will be used to calculate the proportion of patients that completed at least 75% of duvelisib doses as documented by the patient pill diaries. The proportion along with an exact 95% confidence interval will be reported.
- 2). Descriptive statistics will be used to calculate the median manufacturing time from the 10 patients that completed at least 75% of duvelisib doses. The median will be reported along with the minimum and maximum manufacturing times.
- 3). A Wilcoxon signed-rank test will evaluate the change in proportion of CD27+/CD28+ and CD4-/CD8- T cells at baseline and at day 15
- 4). Descriptive statistics will be used to calculate the *in vivo* expansion and persistence of CAR-T 19 cells post infusion as measured by serial CAR-T 19 PCR measurements.
- 5). The ORR (complete response or partial response) will be summarized along with an exact 95% confidence interval. Disease response will be based on the RECIST criteria (version 1.1). Please see section 8.2 on the definitions of disease response.

6). The 90 day PFS and OS will be estimated using the Kaplan-Meier method and calculated with corresponding 95% confidence intervals. Please see section 8.3 on the definitions of progressive disease.

7). Descriptive statistics will be used to calculate the frequency of ICU transfers due to CRS and/or neurotoxicity. Descriptive statistics will also be used to calculate the frequency of administration of tocilizumab and/or corticosteroids use for CRS and/or neurotoxicity.

8). Descriptive statistics will be used to assess the frequency of all grade toxicities as defined by CTCAE (version 5.0).

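### Section 7.1 replaces patients whose collection fails after duvelisib, in conflict with the evaluability rules in 17.5.1 and 17.5.2, and 17.5.3 item 2 has no place for failures

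*Combined protocol and SAP*

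**What the plan says.** Section 7.1 allows a second leukapheresis when the first yields too little, and then states: "If patients are not able to collect enough product after the second leukapheresis, they will be considered unevaluable and replaced". It does not say for which endpoint.

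The statistical plan sets evaluability differently. Section 17.5.1 gives two reasons for being unevaluable: too few duvelisib doses, and late leukapheresis ("Patients who do not undergo leukapheresis within two (2) days of completion of the 8 to 15 days of duvelisib will be considered unevaluable"). Section 17.5.2 puts into the primary analysis "All patients that complete >75% of planned duvelisib doses and undergo leukapheresis within 2 weeks" of finishing duvelisib. Neither section sets a condition on cell yield. Section 5.7 says that leukocyte immunophenotyping "will be done at screening and prior to apheresis for manufacturing CAR-T cells".

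The manufacturing endpoint in the Synopsis, repeated in Section 2, is "Manufacturing time of CAR-T 19 cells in weeks (includes manufacturing failure", with the bracket closing there. Section 17.5.3 item 2 analyses it as the "median manufacturing time from the 10 patients that completed at least 75% of duvelisib doses", with the minimum and maximum. The planned size is 20 in the Synopsis, Section 12 and 17.5.2.

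**The concern.** Leukapheresis comes after 8 to 15 days of duvelisib, so the number of cells collected may be affected by the drug. Dropping and replacing patients on that result conditions the analysis on a post-treatment outcome. If duvelisib impaired collection, a report that followed 7.1 literally would not show it.

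The manufacturing question matters to this trial although it is secondary. Section 3.1 gives as part of its motivation that "there are subset of patients that fail to manufacture a sufficient amount of CAR-T cells ex vivo", and 17.5.1 opens by naming shorter manufacturing time among the things examined. Yet no failure proportion is planned, and no text says whether a failed collection counts as a manufacturing failure.

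For the primary endpoint, one patient can be in under 17.5.2 and out under 7.1. If this is left open, the choice could be made after the fold-changes are known.

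**Working it through.** **1. The rules side by side.** Take a patient who took enough doses, had leukapheresis in time, and yielded too little twice.

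| Section | Condition | Status of this patient |
|---|---|---|
| 7.1 | Enough product after at most two collections | Unevaluable, replaced |
| 17.5.1 | Doses received; leukapheresis within 2 days | Evaluable |
| 17.5.2 | More than 75% of doses; leukapheresis within 2 weeks | In the primary analysis |

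The 2-day and 2-week windows also disagree and must be reconciled, but neither concerns yield.

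**2. Can the primary value exist?** Under 5.7, yes, because the second sample precedes apheresis. There is a caveat. The Section 1.3 schedule and 17.5.2 put that sample at day 15 (±2 days in Section 1.3, so days 13 to 17). After an 8-day course with apheresis within two days, apheresis falls by day 10, before that window. The value is therefore available if sampling follows 5.7.

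**3. The plan's own figures.** The sample size of 20 has no stated alpha, power, null value or standard deviation, so there is no calculation to reproduce. The promising rule is at least a two-fold increase in at least 75% of patients: 0.75 × 20 = 15.

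**4. Collection failures.** The documents give no rate, so the number of failures k beside 20 successful collections is an assumption. With replacement the report shows 0/20; the exact upper limit is 1 − 0.025^(1/20) = 16.8%. With failures kept, the observed proportion is k/(20 + k), with Clopper-Pearson limits:

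| k | Under 7.1 | Failures kept | Exact 95% CI |
|---|---|---|---|
| 1 | 0/20 | 1/21 = 4.8% | 0.1-23.8% |
| 2 | 0/20 | 2/22 = 9.1% | 1.1-29.2% |
| 3 | 0/20 | 3/23 = 13.0% | 2.8-33.6% |
| 5 | 0/20 | 5/25 = 20.0% | 6.8-40.7% |

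**5. The promising rule.** Start from 15/20. If r of the k failed-collection patients had a two-fold increase, the proportion is (15 + r)/(20 + k), with r from 0 to k:

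| k | Lowest (r = 0) | Highest (r = k) | Needed for 75% |
|---|---|---|---|
| 1 | 15/21 = 71.4% | 16/21 = 76.2% | 16 |
| 2 | 15/22 = 68.2% | 17/22 = 77.3% | 17 |
| 3 | 15/23 = 65.2% | 18/23 = 78.3% | 18 |

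The call depends on those patients' own fold-changes.

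**6. Manufacturing time.** Item 2 gives only a median, minimum and maximum, with no rule for a patient without a product. A median can take failures if they are ranked as longest. Its position in the ordered list is (n + 1)/2: 10.5 for n = 20, 11.5 for n = 22 (two failures), 13 for n = 25 (five failures). A maximum cannot take them, because a failure has no time.

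**The case against.** The strongest reply is that this is a pilot for estimation only. Section 17.5.2 makes no formal evaluation against a null value, the promising rule is an informal benchmark, and 17.5.1 keeps every patient exposed to duvelisib evaluable for toxicity. All of that stands and limits the severity.

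A reader might also infer more than the documents support:

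- *That failed collections are removed from the primary analysis.* This is not settled. Section 17.5.2 would include these patients, so the documents contradict each other.
- *That this is the failure the trial exists to detect.* The primary objective is phenotype change and manufacturing time is secondary. Section 3.1 speaks of failed manufacture, poor expansion and lost persistence, not of failed collection.
- *That patients are replaced until 20 products succeed.* The sentence covers insufficient collection only. Section 7.1 sends incoming material or final product that misses specification to case-by-case discussion and does not call those patients unevaluable.
- *That the responder proportion is biased upward.* The collection target is a white-cell count, while the primary endpoint is a within-patient fold increase in a T-cell proportion. Nothing in the documents links low yield to a small fold increase. Upward bias is possible, but so is the reverse.
- *That half the data would be discarded.* The count of 10 in item 2 is a numerical inconsistency with the planned 20 and is separate from the replacement rule. It is not evidence of an intended subset.

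**Conclusion.** The point holds in this form. The replacement rule in 7.1 selects on a post-duvelisib outcome and contradicts the evaluability rules in 17.5.1 and 17.5.2. Read literally, it fixes the reported collection failures at zero. With 1 to 3 assumed failures beside 20 successes, the proportion hidden is 4.8% to 13.0%. At the 15/20 threshold, two such patients move the responder proportion to somewhere between 68.2% and 77.3%. These figures rest on assumed failure counts, and the second also on pre-apheresis samples being available.

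Separately, item 2 of 17.5.3 gives no way to show the failures its endpoint is said to include, and it cites the wrong number of patients. This should be corrected before analysis, but in an estimation-only pilot it ranks below the faults that must be fixed for the trial to be interpretable.

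**What to change.** 1. **Sections 7.1, 17.5.1 and 17.5.2.** Reconcile them so that replacement only fills numbers. State that every otherwise evaluable patient with both phenotype samples stays in the primary analysis, whatever the cell yield. The primary denominator may then exceed 20; the 75% rule already works as a proportion.
2. **Failures.** Report collection failures and manufacturing failures as two separate proportions, each with an exact 95% CI, over all patients who undergo leukapheresis.
3. **Section 17.5.3 item 2.** Replace the count of 10 with all patients who meet the dosing criterion and undergo leukapheresis. Give the median time with failures ranked as longest, and the minimum and maximum among successful products only.

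The cost is wording: no new data and no change to patient care. The manufacturing and responder figures may look slightly less favourable.
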